6.2.2 Enrollment, PK testing, and/or Randomization

Enrollment

Participants who are judged to be eligible to participate by the study physician following all screening procedures will be contacted and scheduled for the PK testing session. At the testing session, participants will be assigned a participant identification number (PID). This PID is linked to their blinded randomization assignment, and linked to their SID.

PK Testing

During the PK testing session (Visit 1) the following assessments will be obtained.

- Current medication use – Participants will provide a listing of any and all medications (prescription and over-the-counter) they have taken since the Screening Session. Anyone who reports using any product listed in Section 4.2 Exclusion Criteria will have the PK testing session rescheduled to allow for a 7-day washout period during which they do not take any of the restricted medications.
- Vital signs – The following vital signs will be recorded as baseline values: heart rate, blood pressure, respiration rate.
- Study product markers – Blood samples will be obtained in order to assess product markers at timed intervals during the 10-hour testing session. Using an indwelling catheter that is inserted in the arm, two samples of blood will be collected at the following intervals following dosing: 0hr, 1 hr, 2 hr, 3 hr, 4 hr, 5 hr, 6 hr, 8 hr, 10 hr. This data collection timing schedule is based on previous research.¹

An exploratory examination of the presence of study product markers in urine will be conducted by collecting random urine samples that are timed, to the extent possible, to blood collection time points. Examination of study product markers in urine is exploratory, and will be conducted with the goal of further informing our understanding of the PK parameters obtained from blood samples. Samples for the measurement of study product markers will be analyzed under the supervision of [name].

- Side effects – Study staff will record occurrence of any side effects during the PK testing session.
- Adverse Events – Any occurrence of an adverse event noted by study staff or reported by a participant will be recorded and categorized by system.

Following all testing session assessments, the appointment time for the follow-up session will be confirmed and the participant will be paid for the testing session.

Randomization

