6.2.4 Follow-up Evaluations

24 hr Evaluation

The following measurements and procedures will be completed at the 24-hour follow-up session.

Visit 2 (24 hours following dosing during the PK Testing Session):

- Vital signs – The following vital signs will be recorded: heart rate, blood pressure, respiration rate.
- Electrocardiogram (ECG) – Standard 12-lead ECGs will be performed at the 24-hour follow-up session. A study physician will review the recording and interpret the findings.
- Laboratory values (CBC, BMP, LFT) – Blood samples will be obtained and CBC, BMP, and LFT assays will be assayed. [name] will review and interpret the lab results.
- Study product markers – Blood and urine samples will be obtained in order to assess level of product markers.
- Side effects – Study staff will record any side effects reported by the participant.
- Adverse Events – Any occurrence of an adverse event reported by a participant will be recorded and categorized by system (i.e., cardiovascular, dermatologic, endocrine/metabolic, gastrointestinal, hematologic, hepatic, musculoskeletal, neurologic, renal, reproductive, or respiratory).

36 hr Follow-up. A phone contact will be made at 36 hours following the dosing time at the PK testing session (i.e., 24 hours following the end of the testing session). During this contact, information regarding any side effects or adverse events that were experienced since the last study visit will be collected.

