9.5 Outcomes

9.5.1 Primary Outcomes

Blood samples will be collected on the time schedule listed in sections 6.2.2 and 6.2.5 above. These samples will be assayed in order to determine the following PK parameters for the study product markers.

C_{\max} (ng/mL) – first maximal concentration,

t_{\max} (h) – time to reach the C_{\max} ,

AUC (0-t) (ng/mL) – Area under the curve, and

Terminal $t_{1/2}$ (h) – terminal half-life.

Measures of the study product markers obtained from the random urine collections will also be examined and compared to the pattern of change seen from the serum samples.

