9.6 Data Analyses

Statistical analyses will be conducted to address the study objective to determine bioavailability and pharmacokinetic properties of product markers after oral consumption of a daily dose of HP extract. The analyses will follow the statistical method used by Loew and colleagues.¹

The maximal concentration (C_{\max}) and the time to reach C_{\max} (t_{\max}) will be computed for each study product marker using the assay values obtained from the repeated serum collections. The area under the curve (AUC) will be calculated using the trapezoidal rule. The terminal half-life ($t_{1/2}$) will be calculated using linear regression from the log-linear slope of at least three concentrations.

In order to test the hypothesis that these values will be enhanced for those who received the HP extract in the enteric coated capsules, the outcome measures for the two groups will be compared.

Analyses of the primary outcome measures (C_{\max} , t_{\max} , AUC, and $t_{1/2}$) will be conducted on the timed interval blood samples collected from 12 participants who complete the study protocol. Missing data, therefore, should not be a significant issue, resulting only from cases of an accident or assay problem with a specific sample. If there is a missing value for a specific timed interval sample for an individual, the missing value will be replaced in one of two ways in order to compute the primary outcome measures. (1) The missing value will be replaced with the average of the surrounding values if the missing value is a sample other than the first or last timed interval sample. (2) The missing value will be replaced with the immediately adjacent value if it is either the first timed sample or the last timed sample.

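### Spot urine is collected without void volume, interval or urine creatinine, so the planned comparison of its time pattern with serum is confounded by dilution (minor, cheap to fix)

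*Protocol*

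**What the plan says.** Protocol 6.2.2 introduces the urine work modestly: "An exploratory examination of the presence of study product markers in urine will be conducted". It obtains the samples by "collecting random urine samples that are timed, to the extent possible, to blood collection time points" and gives the purpose as helping to understand the PK parameters from blood. It states the status plainly: "Examination of study product markers in urine is exploratory".

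Two later sections ask more of the same samples. For the 24-hour visit, 6.2.4 says "Blood and urine samples will be obtained in order to assess level of product markers". Section 9.5.1, headed Primary Outcomes, lists Cmax, tmax, AUC and terminal half-life from blood, and then says that the urine measures will be examined and "compared to the pattern of change seen from the serum samples".

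Section 9.6 bases the analysis of the primary measures on blood alone: it "will be conducted on the timed interval blood samples collected from 12 participants who complete the study protocol". The Primary Outcomes list in section 3 also contains only the four PK metrics. Section 9.5.2 says there are no secondary outcomes, and 9.5 has no exploratory heading.

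No section mentions urine volume, the interval since the last void, an initial void, urine creatinine or specific gravity. Creatinine appears only as a safety parameter in 7.1.

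**The concern.** The concentration of a marker in spot urine is the amount excreted since the previous void divided by the volume produced over that time. Without the volume, or a substitute such as creatinine, a change in concentration may reflect a change in excretion, in urine flow, or in both. A dilute sample looks like falling excretion, and a concentrated one can look like a second peak. Presence can be read from such samples, but level over time cannot be read reliably.

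What is at stake is the comparison with the serum pattern in 9.5.1, and with it the aim in 6.2.2 of using urine to help interpret the blood results. The gap arises at collection. Void times, void volumes and an initial void exist only if they are recorded on the day, so a later analysis plan cannot recover them.

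There is also a labelling inconsistency: 6.2.2 calls the urine measure exploratory, while 9.5.1 places it under Primary Outcomes.

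**Working it through.** The plan gives no figure for the urine work, so there is none to reproduce. The check asks how large dilution could be relative to the signal.

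**Inputs from the protocol**
- Reference peak time 1.3 h and half-life 5.6 h (9.2, from the cited healthy-volunteer study of harpagoside).
- Blood times after dosing: 1, 2, 3, 4, 5, 6, 8 and 10 h (6.2.2) and 24 h (6.2.4). The 0 h sample is left out because the modelled concentration is zero there.

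**Assumptions not in the documents**
- The CV of urine flow between one person's samples is 30% to 150%, with log-normal variation that is independent between samples.
- Serum follows a one-compartment oral curve, and urine concentration is proportional to serum concentration divided by urine flow.

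**Step 1: size of the serum signal.** The elimination rate is ke = ln 2 / 5.6 = 0.124 per hour. Solving ln(ka/ke)/(ka − ke) = 1.3 gives ka = 2.41 per hour. The curve exp(−ke·t) − exp(−ka·t) then falls from its peak about 2.8-fold by 10 h and 15.8-fold by 24 h. Simple exponential decay from the peak gives similar values: 2^((10 − 1.3)/5.6) = 2.94 and 2^((24 − 1.3)/5.6) = 16.6.

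**Step 2: variance of log serum over the sampling times.** It is 0.128 for 1 to 10 h and 0.726 for 1 to 24 h.

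**Step 3: share due to dilution.** The log-variance of flow is ln(1 + CV²), so

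share = ln(1 + CV²) / [ln(1 + CV²) + variance of log serum].

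For example, at CV 50%, ln(1.25) = 0.223. The share is 0.223/(0.223 + 0.128) = 64% for 1 to 10 h and 0.223/(0.223 + 0.726) = 24% for 1 to 24 h.

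| Assumed flow CV | Share, 1–10 h | Share, 1–24 h |
|---|---|---|
| 30% | 40% | 11% |
| 50% | 64% | 24% |
| 80% | 80% | 41% |
| 100% | 84% | 49% |
| 150% | 90% | 62% |

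**Step 4: where dilution reaches half.** Setting ln(1 + CV²) equal to the variance of log serum gives CV = √(e^0.128 − 1), about 37%, for 1 to 10 h, and √(e^0.726 − 1), about 103%, for 1 to 24 h.

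**The case against.** The stated aim in 6.2.2 is presence, and dilution hardly affects that, detection limits aside. The rise from a pre-dose sample without marker to first appearance is also something dilution cannot imitate. Both points stand. They do not cover the level at 24 h or the pattern comparison in 9.5.1.

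The protocol nowhere says that raw concentration will be used. Section 3 refers to standard processing protocols for serum and urine, and creatinine could be specified in an assay procedure or an analysis plan. This stands in part: creatinine could be measured later if aliquots are kept, which the protocol does not specify. Void volume, interval and an initial void could not be recovered.

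Three stronger readings are tempting, and the documents do not support them.

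- A reader might infer that the urine series mainly shows how much people drank. That depends entirely on an assumed flow variation. It is plausible for 1 to 10 h, but with the 24-hour sample included it needs a flow CV above about 100%.
- A reader might infer that differences in fluid intake could pass for a capsule effect. No enteric versus non-enteric comparison of urine is explicitly planned. Assignment is randomised and blinded, so intake should not differ systematically by arm, although chance imbalance is possible with six per arm.
- A reader might infer that 9.5.1 makes urine a primary endpoint. Sections 3 and 9.6 confine the primary outcomes to four PK metrics, 9.6 takes them from blood, and 6.2.2 says exploratory. The placement is a labelling inconsistency.

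**Conclusion.** The point holds as a minor one. As written, the comparison of urine with the serum time pattern is confounded by dilution and is unreliable within the 10-hour session, where nine of the ten blood times fall. The estimated share of within-person log-variance due to dilution, 40% to 90% over 1 to 10 h and 11% to 62% with the 24-hour sample, rests on an assumed flow CV of 30% to 150% and on reference values for harpagoside in healthy volunteers. The other markers may behave differently. No primary PK estimate changes, and no planned test or decision depends on the urine data.

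**What to change.** In 6.2.2 and 6.2.4, choose one of the following before the first session:

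1. Have participants empty the bladder at 0 h, record the time and volume of each void, and compare the amount excreted per interval with serum.
2. Measure creatinine in each urine aliquot and compare the marker/creatinine ratio with serum. Recording void times as well is worthwhile, because the ratio still averages over the time since the previous void.
3. Limit urine to presence or absence, and delete the pattern comparison from 9.5.1.

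Whichever is chosen, move the urine sentence out of 9.5.1 to an exploratory heading, in line with 6.2.2.

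Cost: the first option needs a few CRF fields, a measuring vessel and a little staff time. The second needs at most about 120 inexpensive assays (10 time points × 12 participants). The third costs nothing but gives up the pattern comparison. None adds a visit.

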6.2.3 Blinding

All study staff who have direct contact with study participants and/or are involved in data collection or analysis, including the PI and the study biostatistician, will be blinded as to randomization assignment into study group. Knowledge of random assignment will remain blinded until all preliminary data reviews and quality checks are completed. [name] will be authorized to break the blind for the DSMB as needed to respond to adverse events.

6.2.4 Follow-up Evaluations

24 hr Evaluation

The following measurements and procedures will be completed at the 24-hour follow-up session.

Visit 2 (24 hours following dosing during the PK Testing Session):

- Vital signs – The following vital signs will be recorded: heart rate, blood pressure, respiration rate.
- Electrocardiogram (ECG) – Standard 12-lead ECGs will be performed at the 24-hour follow-up session. A study physician will review the recording and interpret the findings.
- Laboratory values (CBC, BMP, LFT) – Blood samples will be obtained and CBC, BMP, and LFT assays will be assayed. [name] will review and interpret the lab results.
- Study product markers – Blood and urine samples will be obtained in order to assess level of product markers.
- Side effects – Study staff will record any side effects reported by the participant.
- Adverse Events – Any occurrence of an adverse event reported by a participant will be recorded and categorized by system (i.e., cardiovascular, dermatologic, endocrine/metabolic, gastrointestinal, hematologic, hepatic, musculoskeletal, neurologic, renal, reproductive, or respiratory).

36 hr Follow-up. A phone contact will be made at 36 hours following the dosing time at the PK testing session (i.e., 24 hours following the end of the testing session). During this contact, information regarding any side effects or adverse events that were experienced since the last study visit will be collected.

7. SAFETY ASSESSMENTS

Any occurrence of a self-reported adverse event will be recorded and categorized by system (i.e., cardiovascular, dermatologic, endocrine/metabolic, gastrointestinal, hematologic, hepatic, musculoskeletal, neurologic, renal, reproductive, or respiratory).

7.1 Specification of Safety Parameters

Safety and potential toxicity of HP extract ingestion will be evaluated by measuring vital signs; capturing adverse events; and, screening for potential renal, hepatic, metabolic, muscle, cardiac and hematological toxicity (by measuring biochemical and hematological parameters and by recording electrocardiograms (ECG)). Based on previous research and standard practice regarding monitoring the use of NSAIDs, CBC, BMP, and LFT assay results will be evaluated as primary safety measures. Examples of parameters that will be indicative of safety concerns include: a clinically meaningful drop in hemoglobin which could indicate GI bleeding; clinically meaningful changes in creatinine; and, clinically meaningful changes in liver function test parameters.

7.2 Methods and Timing for Assessing, Recording, and Analyzing Safety Parameters

H. procumbens (Devil's Claw) is a widely-prescribed product in Europe and is widely-available in the United States in grocery stores, health food stores, and pharmacies. Numerous reviews provide a summary of safety-related information.^{3,10,34-41} Previous research using dose levels in the range of 50-100mg harpagoside daily dose has shown it to be at least as well tolerated as more traditional pain medication (e.g., nonsteroidal anti-inflammatory drugs),^{8,9} and allergies have been rare. Potential side effects of *H. procumbens* (Devil's Claw) include mild gastrointestinal symptoms such as diarrhea, nausea, vomiting, abdominal pain; headaches; ringing in the ears; loss of appetite; and, loss of taste. It may also be related to allergic skin reactions, menstrual problems, and changes in blood pressure.⁴¹

Screening criteria address possible risks by excluding people with conditions that might be contraindicated. We will monitor possible side effects and adverse events during the testing session and at each follow-up contact, and participants will be given a phone number to contact study staff and/or the investigators to report side effects or adverse events, if needed. Any problems needing medical attention will immediately be triaged by [name] and when appropriate, referred to the participant's personal physician or other appropriate health care providers.

Laboratory-based safety measures and the ECG will be assessed at the screening session to determine eligibility and at the 24-hour follow-up session (Visit 2) to assess health status following dosing. Vital signs will be collected at each study visit. Self-reported adverse events and side effects will be recorded at the follow-up sessions, and participants will be instructed to contact a member of the study team at any time during participation to report an adverse event.

7.3 Adverse Events and Serious Adverse Events

The following definitions will be used in the study when recording adverse events (AE), serious adverse events (SAE), and Unanticipated Problems.

An adverse event (AE) is any untoward medical occurrence to a subject during participation in the clinical study. This can include a sign, symptom, abnormal assessment (laboratory test value, vital signs, electrocardiogram finding, etc.), or any combination of these regardless of relationship to participation in the study.

SAE will be defined as any untoward medical occurrence that results in death, is life threatening, requires inpatient hospitalization or prolongation of existing hospitalization, results in persistent or significant disability/incapacity. An important medical event that may not result in death, be life threatening, or require hospitalization may be considered an SAE when, based upon appropriate medical judgment, the event may jeopardize the subject and may require medical or surgical intervention to prevent one of the outcomes listed in this definition.

Unanticipated Problems are those that involve risks to participants to include, in general, any incident, experience, or outcome that meets all of the following criteria:

- Unexpected in terms of nature, severity, or frequency given (a) the research procedures that are described in the protocol-related documents, such as the IRB-approved research protocol and informed consent document, and (b) the characteristics of the participant population being studied;
- Related or possibly related to participation in the research (“possibly related” means there is a reasonable possibility that the incident, experience, or outcome may have been caused by the procedures involved in the research); and,
- Suggests that the research places participants or others at a greater risk of harm (including physical, psychological, economic, or social harm) than was previously known or recognized.

Laboratory values from CBC, BMP, and LFT assays will be examined. Any values that indicate a safety concern will be identified, reported to a study physician within 48 hours of the laboratory report being received by study staff, and followed-up by a study physician within 48 hours of notification. Abnormal laboratory values will be defined as values that are outside the reference range for a laboratory.

Participants will be given the name and phone number for study staff to report any adverse event that occurs. In addition, participants will be asked at the follow-up study session (Visit 2) and the follow-up phone contact to report any side effect or adverse event that might have occurred since the previous report. The timing of any reported adverse event will be recorded to ensure that an AE is not recorded as two separate events.

7.4 Reporting Procedures

[name] will review all AE/SAE related data within 24 hours of data collection. Any problems needing medical attention will be triaged by [name], and when appropriate, referred to the patient's personal physician or other health care providers. [name] and [name] will determine whether an AE is expected or unexpected. An AE will be considered unexpected if the nature, severity, or frequency of the event is not consistent with the risk information previously described for *H. procumbens*.

[name] will record all reportable events with start dates occurring any time after informed consent is obtained until 7 (for non-serious AEs) or 30 days (for SAEs) after the last day of study participation. Unanticipated Problems will be recorded in the data collection system throughout the study. At each study visit/contact, the investigator will inquire about the occurrence of AE/SAE since the last visit. Events will be followed for outcome information until resolution or stabilization.

[name] will report to the DSMB and IRB unanticipated problems using the following guidelines.

- Unanticipated AE/SAE resulting in death – within 24 hours of becoming aware of the event.
- Unanticipated SAE not resulting in death – within 24 hours of becoming aware of the event.
- All other AE that meet the definition of an Unanticipated Problem – within 5 business days of notification of the event.

[name] will report all AE/SAE to the DSMB, IRB, FDA and NCCIH in accordance with requirements.

- 7-day IND Safety Report (unexpected fatal or life-threatening AE related to HP extract); a copy of the report sent to the FDA will be submitted to the NCCIH Program Officer within 24 hours of FDA notification.
- 15-day IND Safety Report (any other serious and unexpected AE related to HP extract); a copy of the report submitted to the FDA will be submitted to the NCCIH Program Officer within 24 hours of FDA notification.
- All other AE documented during the course of the trial will be reported to NCCIH on an annual basis by way of inclusion in the annual report and in the annual AE summary which also will be provided to the FDA, IRB and the DSMB.

7.5 Follow-up for Adverse Events

[name] will record all reportable events with start dates occurring any time after informed consent is obtained until 7 (for non-serious AEs) or 30 days (for SAEs) after the last day of study participation. Events will be followed for outcome information until resolution or stabilization.

